4.4. Secondary Endpoints Analysis

Unless otherwise specified, secondary efficacy analyses will be conducted for EAS. Decision will be guided by the 2-sided p-values in each objective (see [Table GZBF.4.4](#)).

Table GZBF.4.4. Secondary Measures Not Controlled for Type 1 Error

Objectives	Relative to the efficacy measure	Analysis conducted in a manner similar to	Additional information
LY3437943 1, 4, 8, or 12 mg is superior to placebo at Week 48 from randomization (Week 0)	Mean percent change in body weight	MMRM model in Section 4.3.2	Same independent variables as in the MMRM model in Section 4.3.2. LSM estimates will be plotted by treatment through 48 weeks.
LY3437943 1, 4, 8, or 12 mg is superior to placebo at various visits from randomization (Week 0)	Percentage of study participants who achieve ≥5% body weight reduction ≥10% body weight reduction ≥15% body weight reduction	Logistic regression model with multiple imputation assuming ignorable missingness (Ma et al. 2022)	Use treatment group, stratification factors and continuous baseline value as covariates. Missing postbaseline continuous-valued body weight data are imputed first within each treatment arm before deriving the binary outcome. Plot of proportion of patients achieving ≥5%, ≥10%, and ≥15% body weight reduction will also be provided. Kaplan-Meier plots of time to initially achieve ≥5%, ≥10%, and ≥15% body weight reduction will be provided.
	Mean change in body weight (kg)	MMRM model in Section 4.3.2 with change in body weight (kg) as the response variable	Same independent variables as in the MMRM model in Section 4.3.2. LSM estimates will be plotted by treatment through 48 weeks.
	Mean change in BMI (kg/m ²)	MMRM model in Section 4.3.2 with change in BMI (kg/m ²) as the response variable	Use baseline BMI (kg/m ²) as a covariate. LSM estimates through 48 weeks will be plotted by study treatment.
	Mean change in waist circumference (cm)	MMRM model in Section 4.3.2 with change in waist circumference (cm) as the response variable	Use baseline waist circumference as a covariate. LSM estimates through 48 weeks will be plotted by study treatment.

Abbreviations: BMI = body mass index; LSM = least squares mean; MMRM = mixed model for repeated measures.

4.4.1. Analyses for Supplemental Estimand(s)

Mean percent change in body weight at Week 48 will also be analyzed by ANHECOVA guided by the hybrid estimand (similar analysis in Section 4.3.3). Missing body weight values at Week 48 will be imputed by the multiple imputation method described in Section 4.3.3.

[figure not shown]
Analysis guided by “adherer estimand” might also be conducted for these endpoints (similar analysis in Section 4.3.3).

4.5. Tertiary/Exploratory Endpoints Analysis

Unless otherwise specified, exploratory analyses will be conducted for EAS. Decision will be guided by the 2-sided p-values in each objective.

Table GZBF.4.5. Exploratory Measures

Objectives	Relative to the efficacy measure	Analysis conducted
Compare LY3437943 1, 4, 8, or 12 mg with placebo at various visits from randomization (Week 0)	Percentage of study participants who achieve 
 • $\geq 20\%$ body weight reduction • $\geq 25\%$ body weight reduction • $\geq 30\%$ body weight reduction 	Same logistic regression model in Table GZBF.4.2 . Plot of proportion of patients achieving $\geq 20\%$, $\geq 25\%$, and $\geq 30\%$ body weight reduction will also be provided. Kaplan-Meier plots of time to initially achieve $\geq 20\%$, $\geq 25\%$, and $\geq 30\%$ body weight reduction will be provided.
Compare LY3437943 1, 4, 8, or 12 mg with placebo at Weeks 24 and 36 from baseline (Week -1)	Mean change in 
 • systolic BP (mmHg) measured by ABPM • diastolic BP (mmHg) measured by ABPM 	Use treatment policy estimand with all the data available in safety analysis set for MMRM model in Section 4.3.2 . If using ANHECOVA model in Section 4.3.3 , multiple imputation will be done by treatment group with all available data in safety analysis set.
	Mean change in heart rate measured by ABPM	Same above.
Compare LY3437943 1, 4, 8, or 12 mg with placebo at Weeks 24 and 48 from randomization (Week 0)	Mean change in the following fasting lipid parameters 
 • total cholesterol • HDL cholesterol • LDL cholesterol • VLDL cholesterol • non-HDL cholesterol • triglycerides 	MMRM model in Section 4.3.2 with baseline response as covariate and log transformation for the response variables. LSM estimates through 48 weeks will be plotted by study treatment.
Compare LY3437943 1, 4, 8, or 12 mg with placebo at Weeks 24, 36 and 48 from randomization (Week 0)	Mean change in 
 • fasting glucose (mg/dL and mmol/L) • HbA1c (% and mmol/mol) 	MMRM model in Section 4.3.2 with baseline response as covariate. LSM estimates through 48 weeks will be plotted by study treatment.
Compare LY3437943 1, 4, 8, or 12 mg with placebo at Weeks 24 and 48 from randomization (Week 0)	Proportion of participants with incident T2D	Logistic regression model in Table GZBF.4.1 with baseline HbA1c as covariate.
Compare LY3437943 1, 4, 8, or 12 mg with placebo at Weeks 24 and 48 from randomization (Week 0)	Mean change in mechanistic biomarkers: 
 • fasting insulin • fasting C-peptide • total adiponectin • CCI • leptin • intact proinsulin • HOMA2-IR • HOMA2-B • intact proinsulin/C-peptide ratio • intact proinsulin/insulin ratio • CCI 	
 • For endpoint biomarkers in the list below, use ANHECOVA model where multiple imputation will use only hypothetical strategy to deal with ICEs. 
 • total adiponectin • CCI • leptin • beta-hydroxybutyrate • uric acid • Apo B • Apo C3 • hsCRP

Objectives	Relative to the efficacy measure	Analysis conducted
	 
 • beta-hydroxybutyrate • free fatty acids • uric acid • Apo B • Apo C3 • hsCRP 	
For longitudinal biomarkers in the list below, MMRM model in Section 4.3.2 with baseline response as covariate.
 
 • fasting insulin • fasting C-peptide • HOMA2-IR • HOMA2-B • intact proinsulin • intact proinsulin/C-peptide ratio • intact proinsulin/insulin ratio • CCl • free fatty acids 
LSM estimates through 48 weeks will be plotted by study treatment.
 
Log transformation of the response variables may be conducted.

Compare LY3437943 1, 4, 8, or 12 mg with placebo at Weeks 24 and 48 from randomization (Week 0)	Proportion of participants with change in PGIS-Physical Function	See Section 4.7.1.1.
Compare LY3437943 1, 4, 8, or 12 mg with placebo at Weeks 24 and 48 from randomization (Week 0)	Mean change in 
 • SF-36v2 acute form domain scores • Eating Inventory domain scores 	See Sections 4.7.1.2 and 4.7.1.3.

Abbreviations: ABPM = ambulatory blood pressure modeling; ANHECOVA = analysis of heterogeneous covariance; Apo B = apolipoprotein B; Apo C3 = apolipoprotein C-III; BP = blood pressure; **CCl** [REDACTED]; HbA1c = glycated hemoglobin A1c; HDL = high-density lipoprotein; HOMA2-B = homeostasis model assessment of beta-cell function; HOMA2-IR = homeostasis model assessment of insulin resistance; hsCRP = high sensitivity C-reactive protein; LDL = low-density lipoprotein; LSM = least squares mean; MMRM = mixed model for repeated measures; PGIS = Patient Global Impression of Status; SF-36v2 = Short Form 36 version 2 Health Survey; T2D = type 2 diabetes mellitus; VLDL = very low-density lipoprotein.

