Summary statistics for categorical measures (including categorized continuous measures) will include sample size, frequency, and percentages. Fisher’s exact test will be used to examine the treatment difference in categorical outcomes. Logistic regression may be used to examine the treatment difference in binary efficacy outcomes. The negative binomial regression model may be used for the treatment comparison of discrete count measures if deemed appropriate.

Participant-specific random effects may be added to the logistic and the negative binomial regression models if longitudinal measurements are available.

Other statistical methods may be used, as appropriate, and details will be documented in the SAP.

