4.1. General Considerations

Statistical analysis of this study will be the responsibility of Eli Lilly and Company (Lilly) or its designee. Some analyses and summaries described in this analysis plan may not be conducted if not warranted by data (eg, few events to justify conducting an analysis). Additional analyses of the data may be conducted as deemed appropriate.

Unless otherwise noted, tests of treatment effects will be conducted at a 2-sided alpha level of 0.05, and the CI will be calculated at 95% 2-sided. All tests of interactions between treatment groups and other factors will be conducted at a 2-sided alpha level of 0.10.

Unless otherwise specified, the efficacy analysis will be conducted using EAS and the safety analysis will be conducted using SS.

Unless stated otherwise, statistical summaries and analyses will be conducted based on planned randomized treatment group: placebo, LY 1.0 mg, LY 4.0 mg (2.0 mg), LY 4.0 mg (4.0 mg), LY 8.0 mg (2.0 mg), LY 8.0 mg (4.0 mg), and LY 12.0 mg (2.0 mg), regardless of the actual treatment(s) received by the participant due to any dose modification. The evaluation of the efficacy and safety endpoints for LY 4.0 mg and LY 8.0 mg compared with placebo or dulaglutide will be made by pooling 2 dose escalation regimens, ie, combine LY 4.0 mg (2.0 mg) and LY 4.0 mg (4.0 mg) as LY 4.0 mg (pooled), and combine LY 8.0 mg (2.0 mg) and LY 8.0 mg (4.0 mg) as LY 8.0 mg (pooled). Therefore, the statistical comparisons will be made between each of LY3437943 treatment groups: LY 1.0 mg, LY 4.0 mg (2.0 mg), LY 4.0 mg (4.0 mg), LY 4.0 mg (pooled), LY 8.0 mg (2.0 mg), LY 8.0 mg (4.0 mg), LY 8.0 mg (pooled), LY 12.0 mg (2.0 mg) and placebo.

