For continuous measures, summary statistics will include sample size, mean, SD, median, minimum, and maximum for both the actual and the change from baseline measurements. LS means and standard errors derived from the analysis models will also be displayed for the change from baseline measurements. Treatment comparisons will be displayed showing the treatment difference LS means and the 95% CIs for the treatment differences, along with the p-values for the treatment comparisons. All baseline measures will be analyzed using an analysis of variance model that has treatment group as the model terms.

For categorical measures, summary statistics will include sample size, frequency, and percentages. A logistic regression model will be used to examine the treatment difference in binary efficacy outcomes with missing endpoints imputed. Fisher's exact test or Pearson's chi-square test will be used for treatment comparisons in other categorical outcomes.

For laboratory values, both CN and SI units will be presented. For body weight, kilogram (kg) will be presented.

Summary statistics for discrete count measures will include sample size, mean, SD, median, minimum, and maximum.

Kaplan-Meier method will be used for estimation of cumulative event-free survival rates over time, and Cox proportional hazards regression analysis will be used to compare hazards rates among treatments. In Kaplan-Meier estimation, the dose-pooling strategy will be used: subjects in the pre-specified analysis set with the same pre-planned titration history will be pooled together to calculate the number of events and the total number of subjects at risk.

Unless otherwise specified, baseline is defined as the last nonmissing measurement prior to first dosing of the study drug, or prior to the randomization date for the subjects who are randomized but never dosed.

End of study participation for a participant will be the earliest of date of death, date of withdrawal from further participation in the study, or date of safety follow-up visit (Visit 801). For participants considered to be lost-to-follow-up, end of study participation will be the date of lost-to-follow-up reported by the investigator. Participant data included in the database after the last date of study participation (including safety follow-up period) will be excluded from statistical analysis.

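### The logistic regression planned for ≥20%, ≥25% and ≥30% weight loss names no method for a placebo arm without responders, where odds-ratio/Wald inference fails

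*SAP*

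**What the plan says.** SAP 4.5, Table GZBF.4.5, gives the method for the ≥20%, ≥25% and ≥30% endpoints as "Same logistic regression model in Table GZBF.4.2". Table GZBF.4.2 holds the intercurrent-event strategies for the hybrid estimand and contains no logistic model. The model evidently meant is the one in SAP 4.4, Table GZBF.4.4, for the 5/10/15% endpoints: "Logistic regression model with multiple imputation assuming ignorable missingness", with treatment group, stratification factors and baseline value as covariates. On imputation, that table says: "Missing postbaseline continuous-valued body weight data are imputed first within each treatment arm before deriving the binary outcome".

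The surrounding rules are these:

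- SAP 4.1: "A logistic regression model will be used to examine the treatment difference in binary efficacy outcomes with missing endpoints imputed". Fisher's and chi-square tests are kept for the other categorical outcomes.
- Protocol 9.4.1: Fisher's "exact test will be used to examine the treatment difference in categorical outcomes", and "Logistic regression may be used to examine the treatment difference in binary efficacy outcomes".
- SAP 4.1 also allows an analysis to be left out when there are "few events to justify conducting an analysis". It gives no trigger and no substitute.
- SAP 4.5, for the exploratory endpoints: "Decision will be guided by the 2-sided p-values in each objective".

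No penalised, exact or other zero-cell method is named for these endpoints. Plots of proportions and Kaplan-Meier plots are planned alongside.

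**The concern.** The model suits 5%, 10% and 15% weight loss, where placebo will almost surely have responders. It is carried over unchanged to thresholds that placebo participants may never reach. When the reference arm has no responder, the likelihood keeps rising as the log-odds ratio grows, so software stops at an arbitrary large value with an enormous standard error.

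Imputation within arm does not prevent this, because missing placebo weights are drawn from the placebo distribution. One empty imputed dataset is enough to spoil Wald-type pooling. Placebo is the comparator for every dose, so a single empty arm affects all the comparisons for that endpoint.

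At stake is an exploratory comparison that is either lost or analysed by a method chosen after the data are seen.

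**Working it through.** **Inputs.** 300 participants at 2:1:1:1:1:2:2 (Protocol 9.2) gives 300 × 2/10 = 60 on placebo and 60 per dose. SD 10, effect -8 at Week 24 and 20% dropout, so 48 completers per arm, come from SAP 5. The documents give no placebo mean; 0 to -5% is assumed, with normality.

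**The plan's own figure.** With 48 per arm, difference 8, SD 10 and two-sided 0.05, noncentral-t power is 97.2%, which agrees with the stated 97%. The plan gives no responder rates.

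**Empty placebo arm, complete data.** p = Φ((-threshold - mean)/10); P(none of 60) = (1 - p)^60. Example at ≥30%, mean 0: p = Φ(-3) = 0.00135, and 0.99865^60 = 92%.

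| Threshold | mean 0 | mean -2 | mean -5 |
|---|---|---|---|
| ≥15% | 1.6% | 0.2% | <0.1% |
| ≥20% | 25% | 11% | 2% |
| ≥25% | 69% | 52% | 25% |
| ≥30% | 92% | 86% | 69% |

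**After imputation.** Simulation with 48 observed and 12 imputed placebo values and 20 imputations (number assumed). The chance that at least one imputed set has no placebo responder is 74-94% at ≥30%, 34-74% at ≥25% and 4-33% at ≥20%.

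**Effect on pooling.** Take 7/60 on a dose, no covariates. This is near the 6.9 expected at ≥25% with placebo mean -5 and the -8 effect. Stopped at 20 Newton-Raphson iterations, a set with 0/60 on placebo gives log-OR 19.2 and variance about 2.69 × 10^7; a set with 1/60 gives 2.05 and 1.18. Rubin's rules average the variances, and the between-set term is negligible beside them:

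- 16 of 20 sets empty: SE ≈ √(0.80 × 2.69 × 10^7) ≈ 4,640; p = 0.997.
- 1 of 20 sets empty: SE ≈ √(0.05 × 2.69 × 10^7) ≈ 1,160; p = 0.998.

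Other summaries of similar data do not break down:

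- Risk difference, same 20 sets, Rubin's rules: 0.80 × 7/60 + 0.20 × 6/60 = 11.3 points, p = 0.008. With one empty set: 0.05 × 7/60 + 0.95 × 6/60 = 10.1 points, p = 0.024.
- Fisher's exact test, single dataset, 0/60 vs 7/60: p = 0.013.
- Ordinary likelihood-ratio test, single dataset, 0/60 vs 10/60: p = 0.0001.
- Firth with combined penalised-likelihood profiles, 16 empty sets: OR 13.6, 95% CI 1.6 to 1,528, p = 0.010.

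**How often it would hide something detectable.** The smallest count giving Fisher p < 0.05 against 0/60 is 6/60 (p = 0.027). Joint probability = (1 - p)^60 × P(Bin(60, pa) ≥ 6), where pa is the responder rate on a dose. At the -8 effect this is 0-3.5% at ≥30%, 3.5-18% at ≥25% and 1.6-18% at ≥20%. Expected responders per 60 on a dose at ≥30% are only 0.8-2.7.

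**Week 48.** SAP 1.1 also places these endpoints at Week 48, and Protocol 4.2 expects weight loss to continue. The plan gives no Week 48 effect. With an assumed -12, SD and placebo means unchanged, the joint probability at ≥30% is about 2-37%.

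**The case against.** The strongest reply is that the SAP never commits to an odds ratio or a Wald test. SAP 4.1 speaks only of the treatment difference, and Table GZBF.4.4 cites a methods paper on binary outcomes derived from an incomplete continuous variable. That paper is not available here and may settle the summary measure and pooling. This stands. A reader might infer that the plan leaves no usable comparison with placebo at all; the documents do not support that, because a risk difference from the same model stays finite.

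Second, the plan has exits: the few-events clause, Fisher's test in the protocol, and the plots. This stands only in part. The clause drops the comparison without a replacement, SAP 4.1 moves binary efficacy outcomes away from Fisher's test, and the plots give no test between arms.

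Third, little is lost at Week 24. At ≥30%, where an empty arm is most likely, there is seldom a difference for any method to detect. That is right at the -8 effect, but it need not hold at Week 48 if the effect is larger.

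Fourth, zero-cell methods can disagree: for 0/60 vs 6/60, Firth with a Wald test gives p = 0.058 and Fisher p = 0.027. That is a reason to name one in advance.

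**Conclusion.** The point holds as a minor gap. The logistic regression carried over to ≥20%, ≥25% and ≥30% fails under odds-ratio/Wald inference whenever an imputed dataset has no placebo responder. On complete data at Week 24 an empty placebo arm is likely at ≥30% (69-92%), possible at ≥25% (25-69%) and less likely at ≥20% (2-25%).

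The mechanism is certain. The probabilities rest on the plan's SD of 10, normal tails and an assumed placebo mean; the imputation figures also assume 20 imputations.

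The consequence is limited. The endpoints are exploratory, ≥30% was added in SAP version 4.0 out of exploratory interest, and at the planned effect an empty placebo arm together with a detectable difference is uncommon at Week 24. Nothing here reaches the primary analysis or the 5/10/15% endpoints, where the chance of an empty placebo arm is at most 1.6% at ≥15% and lower below that.

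Separately, the model references in Table GZBF.4.5 are wrong: Table GZBF.4.2 holds estimand strategies, and Table GZBF.4.1, cited for incident T2D, lists disposition reasons.

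**What to change.** In Table GZBF.4.5, before unblinding:

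1. For all three thresholds, with no data-dependent trigger, specify Firth-penalised logistic regression with the same covariates and penalised-likelihood inference, combined over imputations.
2. Report the difference in proportions against placebo with a 95% CI that is valid with zero cells.
3. Where neither compared arm has a responder, give the counts alone.
4. Editorial: point the model references for these endpoints and for incident T2D to Table GZBF.4.4.

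Leave the primary and 5/10/15% analyses as planned.

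The cost is SAP wording and some extra programming to combine penalised-likelihood results over imputations. Odds ratios shrink slightly towards 1, and upper limits stay very wide when placebo is empty, as the interval of 1.6 to 1,528 shows.

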4.5.1. Pharmacokinetic and Pharmacokinetic/Pharmacodynamic Methods

Pharmacokinetic, PD, and PK/PD analysis are the responsibility of Lilly's PK/PD group.

LY3437943 concentration-time data will be summarized in the CSR. Exposure-response analysis between LY3437943 concentration and safety, pharmacology, and efficacy may be performed using population PK and population PK/PD nonlinear mixed-effects modeling techniques implemented on Nonlinear Mixed Effects Modeling software. Additionally, the impact of intrinsic and extrinsic factors (such as age, weight, sex, renal, and hepatic functions) on PK and/or PD parameters may be evaluated.

4.5.2. Bayesian Analyses for Dose-Response

The longitudinal dose-response model as proposed by Qu et al. (2019) will be adapted here. This model also considers the preplanned dose changes that occur during the titration period. Let $\theta = (\theta_1, \theta_2, \dots, \theta_m)$ be the doses a participant has planned to take and $t_c = (t_{c1}, t_{c2}, \dots, t_{cm})$ be the corresponding times when the dose changes where t_{ci} indicates the time for dose to change from θ_i to θ_{i+1} . Therefore, the mean function of the parameter of interest at time t is modelled by:

$$f_{\theta, t_c}(t) = f(t; \theta_1) + \sum_{i=1}^{m-1} [f(t - t_{ci}; \theta_{i+1}) - f(t - t_{ci}; \theta_i)]I(t > t_{ci}),$$

where $I(X)$ is the indicator function that takes value 1 when the condition X holds. The $f(t; \theta)$ is defined such that

$$f(t; \theta) = \frac{\lambda(\theta)(1 - e^{-k(\theta)t})}{1 - e^{-k(\theta)d}},$$

where d is the maximum duration of the treatment period in weeks ($d = 24$ for primary analyses while $d = 36$ for final analysis), $\lambda(\theta)$ is the dose-response function for the maximum response at dose θ and $k(\theta)$ is dose θ 's rate parameter. This formulation of the mean function $f(t; \theta)$ was introduced by Fu and Manner (2010) to characterize the change from baseline over time in a continuous outcome that could be approximated with a pattern of exponential decay. It assumes a monotone time profile with the maximum effect reached at time d . The longitudinal data $Y_{\theta, t_c, jt}$ for participant j at time t with titration scheme (θ, t_c) will be fitted by adding the error terms to the mean function $f_{\theta, t_c}(t)$ where

$$Y_{\theta, t_c, jt} = f_{\theta, t_c}(t) + \frac{s_j(1 - e^{-k(\theta_1)t})}{1 - e^{-k(\theta_1)d}} + \epsilon_{jt},$$

$s_j \sim N(0, \sigma_s^2)$ and $\epsilon_{jt} \sim N(0, \sigma^2)$ are independent, denoting between-subject variation and within-subject variation respectively. Given s_j , $Y_{\theta, t_c, jt} \sim N(f_{\theta, t_c}(t) + \frac{s_j(1 - e^{-k(\theta_1)t})}{(1 - e^{-k(\theta_1)d})}, \sigma^2)$.

For characterizing the body weight change, we use a different formulation of $f_{\theta, t_c}(t)$ that showed better fitting in the analyses of historical trials and simulation studies while keeping all other elements unchanged. In the new formulation,

$$f_{\theta, t_c}(t) = f(t; \theta_1) + \sum_{i=1}^{m-1} h(t - t_{ci})[f(t; \theta_{i+1}) - f(t; \theta_i)]I(t > t_{ci}),$$

Where $h(t - t_{ci}) = \frac{(1 - e^{-\tau(t - t_{ci})})}{1 - e^{-\tau d}}$. The parameter τ controls the rate of change in the body weight when dose changes. The dose-maximum response function $\lambda(\theta)$ is provided below:

The dose-maximum response function $\lambda(\theta)$ is provided below:

- body weight.

A power model is assumed where

$$\lambda(\theta) = a + b * \theta^\gamma$$

γ is a sigmoidicity parameter indicating shape or steepness of dose response.

Other dose-response models for $\lambda(\theta)$ may be explored if the aforementioned dose-response models do not fit the data well, eg, Simple Normal Dynamic Linear Modeling. Additionally, the different formulation of $f_{\theta, t_c}(t)$ may also be considered if the current specification does not provide an adequate fit to the data.

The estimation of those parameters will be carried out in a Bayesian framework assuming noninformative priors for the hyperparameters in the model as follows:

$$\begin{cases} k(\theta) \sim \text{Uniform}(0,1), \\ \alpha_0, \alpha_1, \alpha_2, a, b \sim N(0, 100^2), \\ 1/\sigma^2, 1/\sigma_s^2 \sim \text{Gamma}(0.01, 0.01), \\ \gamma \sim N(1, 5). \end{cases}$$

Posterior inference will be drawn for the dose-response at time t of clinical interest and the 95% credible intervals will also be plotted.

